14.4 Methods of Analysis

14.4.1 Primary Outcome Measure

The proportion of subjects with ABR = 0 in the 2 prophylaxis treatment regimens in the second 6 months period will be compared using a chi-square test with continuity correction at a 2-sided 5% level of significance.

The null hypotheses of no difference between the prophylactic regimens will be tested against a 2-sided alternative.

The observation period for the primary endpoint will be the second 6 months of prophylaxis (Day 183 to Day 364). If the subject undergoes a surgical procedure the observation period is interrupted starting from the presurgical loading dose until the subject resumes his previous prophylactic treatment regimen, or until rehabilitation or any other surgery specific postoperative measures have been completed, whichever occurs last.

Data analyses will follow the intent-to-treat principle, i.e., bleedings observed in the observation period will be used in the analyses irrespective of compliance with the treatment regimen of the protocol. Only if a subject refuses to provide any bleeding data, the multiple imputations (MI) technique will be used to handle observation periods shorter than 6 months, i.e., 182 days, as follows.

For subjects who terminated before Day 364 and refuse to provide data on bleeds, bleeds will be imputed for the unobserved period from a Poisson random variate. The subject specific Poisson parameter will be determined from estimating a negative binomial model for the bleed rate in the unobserved period with stratum, age, race as well as the number of bleeds from Day 92 to the end of the observed period of the subject as covariates in all subjects of the same Study Arm. For subjects with more than 21 weeks in the observation period, the number of bleeds occurring at a later time in other subjects might be very low or even zero. To avoid estimating from an unstable model, the negative binomial model will be for the number of bleed up to Day 329 with covariates of stratum, age, race and number of bleeds observed from Day 92 to Day 329. At least 1000 imputation datasets will be generated. The chi-squared test statistics with continuity correction and its standard error will be used to compare the 2 study arms in each imputation dataset and the multiple imputations techniques will be used to derive an overall estimate with 2-sided 95% CIs.

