2.3 Sample Size and Power Calculations

For the sample size assessment the following assumptions were used. Approximately 40% of subjects in BAX 855 regimen targeting 1-3% trough level are expected to be bleed-free as shown in the ADVATE Prophylaxis study and the BAX 855 pivotal study 261201. For the BAX 855 regimen targeting approximately 10% (8-12%) trough level, an increase to 70% bleed-free subjects is expected based on modeling the bleeding rates per FVIII level in the BAX 855 pivotal study 261201.

Under these assumptions 48 subjects per study arm are needed to reject the null hypothesis of no difference between the study arms against a two-sided alternative at the 5% level of statistical significance with 80% power. Assuming a drop-out rate of close to 10%, and 10-15% of subjects being non-compliant, approximately 116 subjects are planned to be randomized between the two BAX 855 regimens with an allocation ratio of 1:1.

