5.5.1 Annualized Bleeding Rate

For all subjects who prematurely discontinued from the study (i.e., before ObsDay 364), and who refuse to provide data on bleeds for the remaining time till ObsDay 364, the number of bleeds (and hence the ABR), will be imputed for the second 6-month period, using Multiple Imputation techniques as described below. The ABR for a subject is calculated as the number of bleeds divided by the observation period under consideration (expressed in years).

The number of bleeds during the missing observation period in PROPEL, will be imputed for subjects taking into account, additional post-PROPEL bleeding information that is provided for the subject. Post-PROPEL bleeding information obtained for a subject (either by the subject or from another BAX 855 study), will be treated as if observed within PROPEL before the imputation procedures.

For simplicity, the imputation process is described below for a single subject (since the imputation will be performed on a subject specific basis), focussing on the period of interest for the primary endpoint (2nd 6-month period). The imputation process is described in step-by-step manner.

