Imputation Period (days) = (Date Corresponding to ObsDay 364 – Imputation Start Date)

Where imputation start date is as defined in section 5.4.2: Extended Observation Period of Efficacy.

- This “imputation period” will be treated/imputed as a Poisson random variate. The following example SAS[®] code can be utilized to obtain an estimate for the Poisson parameter:

```
Data <ImpSet>;  
  Set <Dataset>;  
  
  <Mu> = exp(1*<Intcpt> + <Beta1>*<sStrat> + <Beta2>*<sRace> +  
            <Beta3>*<sBAge> + <Beta4>*<sOB> + <LIP>);  
  Do i = 1 to 1 000  
    <ImpUB> = Ranpoi(1234,mu);  
    Iteration = i;  
    Output;  
  End;  
Run;
```

Where <Impset> represents the resultant dataset containing the 1 000 imputed bleed count values. <Dataset> is the input dataset containing the parameter estimates obtained from fitting the Negative binomial as discussed above and <Mu> our Poisson parameter as defined above. <Beta1>, <Beta2>, <Beta3> and <Beta4> the parameter estimates for <Stratn>, <Racen>, <BAge> and <OB> respectively. <sStratn>, <sRacen>, <sBAge> and <sOB> hold values specific to the subject being imputed, for numeric stratum category, numeric race category, baseline age and observed bleeds from ObsDay92 till last ObsDay for the subject, respectively. <LIP> is the logarithm of the imputation period (days) for the subject being imputed and <ImpUB> is the imputed number of bleeds during the imputation period for the subject.

Step3: Adding of Imputed Values to the Observed Values

The imputed bleed count of the subject is added to the subject’s observed bleed count (i.e. the subject’s observed bleeds after ObsDay 182), to obtain a bleed count for the complete 2nd 6-month period of the subject.

$$\text{Complete period bleeds} = \text{Observed period bleeds} + \text{Bleeds for imputation period}$$

For each subject to be imputed, the 1 000 imputed values will be merged into the full subject dataset, thus creating 1 000 replicates of imputed (complete) data sets (one for each imputation iteration).

Step4: Calculating ABR and Categorization

From this step onward we are working with all the subjects (those imputed and those not needing imputation) in the same dataset (1 000 replicates of them).

ABR is calculated as:

$$ABR = \frac{(Observed\ Number\ of\ bleeds + Imputed\ number\ of\ bleeds)}{Period\ under\ consideration\ in\ years}$$

Where period under consideration is:

- 1 year (365.2425 days) when working with the full year.

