- 0.5 years (182 days) when working with the second 6-month period.

For presentations using unimputed ABR:

$$Unimputed\ ABR = \frac{Number\ of\ bleeds\ observed\ within\ PROPEL}{Period\ under\ consideration\ in\ years}$$

A numeric categorical variable for imputed ABR during the complete planned treatment period will be derived as follows:

- Category 1: ABR = 0.
- Category 2: ABR > 0.

Step5: Analysis of Imputed Data Sets

Chi-squared statistics with continuity correction should be calculated for each of the thousand complete datasets on the ABR categorical variable with treatment arm as fixed effect. The following SAS® code can be used:

```
Proc Freq Data = <Dataset>;  
  By <Iter>;  
  Tables <ABRCat>*<Trt> / chisq alpha = 0.05 relrisk riskdiff expected;  
  exact or;  
  Ods Output Chisq = <Outdata>;  
Run;
```

Where <Dataset> is the input dataset containing the 1 000 iterations of the completed

data, <Iter> the iteration number, <ABRCat> the numeric ABR category variable, <Trt> the treatment arm and <Outdata> the output dataset containing the continuity adjusted chi-squared statistics.

Step6: Combining of Statistical Results

An approximately Gaussian test statistic will be derived as the square root of the chi-squared statistic with continuity correction and 1 degree of freedom, with the sign set according to the direction of the effect (proportion higher in treatment arm one [High level] than in treatment arm two [Low level]; zero if equal). That is, if the risk difference of the High Level Arm minus the Low Level arm provided by SAS[®] is larger than naught then the sign to retain will be positive and vice versa.

This needs to be done so the requirements of Rubin's rules are met and the SAS procedure PROC MIANALYZE can be used.

The resultant 1 000 approximately Gaussian test statistics will be summarized using the SAS[®] procedure MIANALYZE. SAS[®] code similar to the below can be utilized:

```
Proc MIanalyze data=<Dataset>;  
  Modeleffects <NormStat>;  
  Stderr <NormSterr>;  
  Ods Output ParameterEstimates = <Outdata>;  
Run ;
```

Where <Dataset> represents the input dataset containing the approximately Gaussian statistics, <NormStat> and <NormSterr> the approximately Gaussian statistics and standard error of 1 respectively and <Outdata> the output dataset containing the overall estimate, 95% confidence interval and corresponding P-value.

Step7: Back Transformation

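### The primary imputation treats the fitted model as known, so Rubin's rules receive too little between-imputation variance; the constant seed may also tie different subjects' draws together (SAP 5.5.1.1, Steps 2 and 6)

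*SAP*

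**What the plan says.** SAP 5.5.1 describes the imputation for one subject, "since the imputation will be performed on a subject specific basis". In 5.5.1.1, Step 1 fits a negative binomial model within the subject's arm (stratum, race, age and earlier bleeds as covariates, with a log-duration offset).

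Step 2 takes a data set that "is the input dataset containing the parameter estimates obtained from fitting the Negative binomial as discussed above", forms Mu from those estimates and the subject's own covariates, and draws 1000 counts with "<ImpUB> = Ranpoi(1234,mu". It introduces the code as an example that may be used. Step 3 merges each imputed subject's 1000 values into the full data, one per iteration. Step 4 says that from there on all subjects are handled in one data set.

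Step 5 computes the continuity-corrected chi-square in each completed data set. Step 6 turns it into a signed z with standard error fixed at 1, so that the requirements of Rubin's rules are met and "the SAS procedure PROC MIANALYZE can be used". Step 7 exponentiates the pooled value and its interval.

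Protocol 14.4.1 also describes a Poisson draw whose parameter comes from a negative binomial model. Its sensitivity paragraph, however, refers to negative binomial distributions being used for the imputations.

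**The concern.** Rubin's rules give a valid total variance only if the imputations reflect everything unknown about the missing values, including uncertainty in the imputation model. Here each of the 1000 draws uses the same Mu. The spread between imputations contains Poisson noise only. Error in the estimated coefficients is left out, and so is the extra-Poisson variation that the fitted model itself estimates.

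The seed is a second, conditional matter. A literal seed in RANPOI sets the stream once per DATA step (general SAS behaviour, taken here as an assumption). If the step is run separately for each imputed subject, every run starts at the same place. After merging by iteration, iteration i uses the same random numbers for all imputed subjects in both arms, whose outcomes then move together instead of independently.

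At stake is the standard error of the primary test. The planned sensitivity analyses (SAP 5.5.1.2 and 7.1.2) inflate the mean, drop post-study bleeds or impute worst case. None changes how the variance is formed, so none would expose either fault.

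**Working it through.** **Inputs from the documents.** The test "will be compared using a chi-square test with continuity correction at a 2-sided 5% level of significance" (Protocol 14.4.1). Sample size "at the 5% level of statistical significance with 80% power" (SAP 2.3). Rates: "Approximately 40% of subjects in BAX 855 regimen targeting 1-3% trough level are expected to be bleed-free" and "an increase to 70% bleed-free subjects is expected" (SAP 2.3). About 116 randomized 1:1, so 58 per arm; dropout close to 10%, so about 6 per arm. 1000 imputations.

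**The plan's own figure.** The standard two-proportion formula gives n = [1.96√(2×0.55×0.45) + 0.842√(0.24+0.21)]² / 0.30² = 42 per arm, or 49 with continuity correction. Exact enumeration of the corrected test at 48 per arm gives 80.05% power, so the stated 48 is reproduced. The documents give no figure for the between-imputation variance.

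**Formula.** MIANALYZE receives z and a standard error of 1, and itself computes B, the variance of the 1000 z values. Pooled SE = √[1 + (1 + 1/1000)B]. For example, B = 0.0774 gives √1.0775 = 1.038.

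**Simulation of Steps 1 to 6.** 400 trials per scenario, 58 per arm. Assumptions not in the documents: dispersion 1, the whole window missing, the numbers imputed, and one uniform number per draw. The reference uses independent streams and draws both coefficients and dispersion. Entries are average pooled SEs, with the difference from the reference.

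| Bleed-free rates; imputed per arm | Reference | Fixed coefficients, no restart | Fixed coefficients, seed restarted |
|---|---|---|---|
| 70/40; 6 and 6 | 1.0445 | 1.0380 (−0.6%) | 1.0527 (+0.8%) |
| same, half the window missing | 1.0275 | 1.0217 (−0.6%) | 1.0247 (−0.3%) |
| same as first row, dispersion 2 | 1.0422 | 1.0345 (−0.7%) | 1.0500 (+0.7%) |
| 70/40; 14 and 14 | 1.1125 | 1.0837 (−2.6%) | 1.2074 (+8.5%) |
| 70/40; 12 and 2 | 1.0579 | 1.0447 (−1.2%) | 1.2355 (+17%) |
| 70/40; 2 and 12 | 1.0530 | 1.0429 (−1.0%) | 1.2087 (+15%) |
| 55/55; 6 and 6 | 1.0393 | 1.0352 (−0.4%) | 1.0188 (−2.0%) |
| 55/55; 14 and 14 | 1.0997 | 1.0789 (−1.9%) | 1.0728 (−2.4%) |
| 55/55; 12 and 2 | 1.0482 | 1.0404 (−0.7%) | 1.1883 (+13%) |

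The fixed coefficients account for nearly all of the shortfall. Drawing them without the dispersion already gives 1.0438 (6 and 6) and 1.1138 (14 and 14). The dispersion hardly moves the SE, though it shifts the average z by up to about 0.1, in either direction.

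**Rejection rates.** For 70/40 with a 12/2 split, the restart lowers rejection from 84.8% to 73.5% (Monte Carlo error about √(0.8×0.2/400) = 2 points); for 2/12, from 81.5% to 79.0%. With equal rates, rejection was 1.8% to 4.8% over all variants (error about 1 point).

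**Why the direction varies.** Suppose all imputed subjects in an arm share one bleed-free probability (0.4 or 0.7), and compare a shared with an independent stream on the difference in proportions. The within-imputation variance is (0.24+0.21)/58 = 0.00776.
- 6 per arm: independent 6×0.45/58² = 0.00080; shared (6/58)²×0.3×0.7 = 0.00225. Total SE is √0.01001 = 0.100 against √0.00856 = 0.0925, or +8%. On the z scale that is pooled, it is 1.120 against 1.046, or +7%.
- 3 per arm: 0.00056 against 0.00040; SE 0.0912 against 0.0903, or +1.0%.
- 2 per arm: 0.00025 against 0.00027; the sign reverses.
- Equal rates and equal numbers: the shared draws cancel and the between-imputation variance of the difference is zero.

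**The case against.** The strongest reply is that the restart is inferred. SAP 5.5.1 says the one-subject description is for simplicity, and the code is an optional template. A single DATA step with one row per imputed subject also fits the text and would not restart the stream. This stands: the restart is not established. It is still the likelier reading, because the Step 2 output is said to hold 1000 imputed counts, which is one subject's worth, and work on all subjects together begins only at Step 4. Nothing warns a programmer against it.

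Second, few subjects will be imputed. Only those who leave early and also give no later bleed data qualify; continuation-study data and leavers' reports count as observed (SAP 7.1.2.1 and 7.1.2.2), and non-compliant subjects are analysed on what was observed. So 6 per arm is near the upper end at planned dropout and 14 is a stress case. This stands too.

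Third, SAP Step 2 follows Protocol 14.4.1 in drawing from a Poisson. That explains the choice but does not make the imputation proper.

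A reader might infer that shared draws always inflate the variance, or that about 8% is the expected error. Neither is supported: the sign depends on rates and balance, and 7–8% at 6 per arm requires every imputed subject in an arm to have the same mean. With covariate-dependent means it is about 1%.

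**Conclusion.** The improper imputation follows from the text: coefficients fixed, dispersion dropped, Rubin's rules applied. Without a restart, the between-imputation variance is too small and the pooled SE is about 0.6% low at 6 imputed per arm and 2.6% low at 14. That is small at planned dropout.

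The seed problem is conditional on one DATA step per subject. If it occurs, the SE is arbitrary: from about 2% too small (equal rates, even imputation) to 8.5% too large at 14 per arm and 17% too large for a 12/2 split. Unequal imputation is plausible in an open-label comparison of every-other-day with roughly twice-weekly infusions. The harm seen is lost power, in a trial planned for 80%.

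Two stronger readings are not supported. Type I error was not seen above 5%. Nor would correcting the draws repair the reported interval: Step 7 exponentiates a pooled z that is not on a log scale, so the result is not an interval for the difference in bleed-free proportions. That is a separate problem.

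All sizes rest on the assumed dispersion, missingness and SAS seed behaviour.

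**What to change.** In Step 2, for each of the 1000 imputations, draw the regression coefficients and dispersion from their estimated sampling distribution (or refit the model on a bootstrap sample), and draw the count from the resulting negative binomial. State that one continuing random stream, or a distinct seed per subject, is used across all imputed subjects. Because Protocol 14.4.1 names a Poisson draw, record the change in SAP 5.8.

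The cost is a few lines of SAS, a sentence or two in the SAP and slightly more computation. Where the seed would not have restarted, the pooled SE rises slightly, which is the intended correction.

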5.5.1.2 Sensitivity Analysis

For the sensitivity analyses, the same imputation procedure as described above will be applied with the Poisson parameter being artificially increased by 10%, 20%, 40% and 80% for all subjects imputed, regardless of their respective treatment arm. Imputation will also be performed as described in Steps one through seven, but with the post-PROPEL bleed data removed.

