The dataset to be analyzed is all subjects. For subjects who developed an inhibitor, missing observation periods will be imputed at twice the rate before the study.

The use of age and race in the imputation model will allow for subgroup analyses of the primary endpoint and ABRs.

Sensitivity analyses

Sensitivity analyses will be performed similar to the primary analysis except that the negative binomial distributions used for imputations will have an artificially increased Poisson parameter by 10%, 20%, 40% and 80%. In addition, a worst-case sensitivity analysis will be performed which imputes worst-case outcomes in all subjects with missing ABR data in the observation period.

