The analysis of this data involves the use of a multiple imputation technique on a transformation of this data. See Section 5.5: Handling of Missing, Unused, and Spurious Data. This is the primary analysis for the PROPEL study.

The primary analysis will be repeated as a sensitivity analysis with the following alternative imputations:

- Standard uninflated imputation (excluding regular post-PROPEL bleeds).
- Imputed bleeds with the mean inflated by 10%.
- Imputed bleeds with the mean inflated by 20%.
- Imputed bleeds with the mean inflated by 40%.
- Imputed bleeds with the mean inflated by 80%.
- Worst case bleed imputation (See Section 5.5: Handling of Missing, Unused, and Spurious Data).

The proportion of subjects with total ABR <2, spontaneous ABR <2, Spontaneous ABR = 0, spontaneous AJBR <2 and spontaneous AJBR = 0, for the second 6-month period (ObsDay 183 to ObsDay364) as well as the full 12-month period treatment period (ObsDay 1 to ObsDay 364), will be analyzed in the same manner as the primary efficacy outcome. The sensitivity analysis described above for the primary efficacy outcome, will not be applicable to the secondary efficacy outcomes.

The total ABR, injury related ABR, spontaneous ABR and spontaneous AJBR, will be analyzed using a generalized linear model fitting a negative binomial distribution with logarithmic link function for the second 6-month period (ObsDay 183 to ObsDay 364) as well as the full 12-month observation period (ObsDay 1 to ObsDay 364). Separate Negative Binomial models will be used for these two time periods. The model is to include the treatment arm assigned (low level or high level), Stratum and race as fixed effects, age at baseline as continuous covariate and the logarithm of the OPE in years as an offset. The following SAS[®] code can be used to perform the analysis:

```
Proc Genmod Data = <Dataset>;
```

```
Class <Treatment> <Strat> <Race> (param=ref ref=first);  
Model <Bleeds> = <Treatment> <PREABR> <Baseline_age> <Race> / type3  
dist = negbin link = log offset = <log_OPE>;  
lsmeans <treatment> / bylevel om CL;  
ODS OUTPUT LSMEANS = <Outdata>;  
Run;
```

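### The sensitivity inflation of imputed bleeds is the same in both arms, so no planned run makes high-trough dropouts worse relative to low-trough dropouts

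*SAP*

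**What the plan says.** The primary endpoint is whether a subject has any bleed from Day 183 to Day 364. Under SAP 5.5.1.1, a subject who leaves early and gives no further bleed data is imputed from a negative binomial model fitted to subjects of his own arm, with stratum, race, age and earlier bleeds as covariates. Bleeds for the missing time are then drawn from a Poisson distribution.

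The sensitivity analyses are:

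- SAP 5.5.1.2: the Poisson parameter is "artificially increased by 10%, 20%, 40% and 80% for all subjects imputed, regardless of their respective treatment arm". Protocol 14.4.1 lists the same four factors and has no arm-specific version.
- SAP 5.5.1.2 and 7.1.2: the imputation is repeated without the bleed data collected after a subject left the study.
- Protocol 14.4.1: a worst case that "imputes worst-case outcomes in all subjects with missing ABR data in the observation period".
- SAP 7.1.2 lists this last run as "Worst case bleed imputation (See Section 5.5: Handling of Missing, Unused, and Spurious Data". Neither 5.5 nor any of its subsections says what the worst-case value is.

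**The concern.** The base imputation treats a high-trough dropout as if he kept the bleed rate of subjects still on the high-trough regimen, given his covariates. That is the assumption most in need of challenge. Protocol 9.3 withdraws subjects for, among other reasons, missing more than 30% of planned doses in a 3-month period or going back to their usual FVIII therapy. Protocol 14.4.1 nevertheless wants bleeds counted irrespective of compliance. If such subjects lose the benefit of the higher trough, their imputed bleed-free probability is too high and the treatment difference is overstated.

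Multiplying the mean by the same factor in both arms does not isolate that possibility, because both proportions fall together. A reader of the report could take a flat series as evidence of robustness to informative dropout on the intensive regimen when that scenario was never run.

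**Working it through.** **Inputs.** SAP 2.3 gives the rates: "Approximately 40% of subjects in BAX 855 regimen targeting 1-3% trough level are expected to be bleed-free", and for the other arm "an increase to 70% bleed-free subjects is expected based on modeling the bleeding rates per FVIII level". It plans about 116 subjects at 1:1, so 58 per arm, with dropout close to 10%. Dropout by arm is not given, so equal dropout is an assumption. So is imputation of the whole 182-day window, which makes the shifts in the high-arm-only and worst-case runs near upper bounds.

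**The plan's own figure.** SAP 2.3 states "48 subjects per study arm are needed to reject the null hypothesis of no difference" "at the 5% level of statistical significance with 80% power", and Protocol 14.4.1 names the test, a "chi-square test with continuity correction at a 2-sided 5% level of significance". Without the correction, n = [1.960·√(2·0.55·0.45) + 0.842·√(0.24 + 0.21)]² / 0.30² = 42.0. With it, n = (42.0/4)·[1 + √(1 + 4/(42.0·0.30))]² = 48.4. Exact power of the corrected test at 48 per arm is 80.05%. The stated 48 is reproduced.

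**Formulas.** For a Poisson count, a bleed-free probability p becomes p^k when the mean is multiplied by k. If only a fraction f of the window is imputed, it becomes p^(1+(k−1)f). With a fraction d of an arm imputed, the arm's proportion is (1−d)·p + d·p^k. The test is z = (|difference| − 1/58) / √(2·p̄(1−p̄)/58), applied to expected proportions. It ignores between-imputation variance, so the p-values are indicative.

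**Whole window imputed, d = 10% in each arm:**

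| Factor | Bleed-free if imputed, low / high (%) | Difference, both arms inflated | Difference, high arm only |
|---|---|---|---|
| 1.0 | 40.0 / 70.0 | 30.0 | 30.0 |
| 1.1 | 36.5 / 67.5 | 30.1 | 29.8 |
| 1.2 | 33.3 / 65.2 | 30.2 | 29.5 |
| 1.4 | 27.7 / 60.7 | 30.3 | 29.1 |
| 1.8 | 19.2 / 52.6 | 30.3 (p = 0.0020) | 28.3 (p = 0.0041) |

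The base p-value is 0.0022. With half the window imputed, high-arm-only 1.8 gives 0.7^1.4 = 60.7%, a loss of about 0.9 points instead of 1.7.

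**More severe assumptions, same setting:**

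- High-trough dropouts at the low-trough rate: 67.0% − 40.0% = 27.0 points, p = 0.0064.
- Planned worst case, every missing subject in both arms bleeds: 63.0% − 36.0% = 27.0 points, p = 0.0065.
- Every missing high-trough subject bleeds, low arm at base: 63.0% − 40.0% = 23.0 points, p = 0.022.
- Missing high-trough subjects bleed and missing low-trough subjects are bleed-free: 63.0% − 46.0% = 17.0 points, p = 0.10.

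If 17.5% of each arm were imputed (assumed), high-arm-only 1.8 gives 27.0 points (p = 0.0064). All missing high-trough subjects bleeding gives 17.8 points (p = 0.084).

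**Direction of the both-arm series.** At factor 1.8 an imputed subject loses 40.0 − 19.2 = 20.8 points in the low arm and 70.0 − 52.6 = 17.4 in the high arm. The ratio is about 1.2, and about 1.4 at factor 1.1. If the high arm has more dropouts than that multiple of the low arm's, the shift reverses: 15% versus 5% dropout gives 28.4 points at 1.8. It also reverses at lower rates (20% versus 50%: 30.0 to 29.3 points). With marked between-subject spread (gamma-mixed means), the difference among dropouts at 1.8 is 29.4 points for dispersion 1 and 28.1 for dispersion 2.

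**Borderline example (assumed 40% versus 60%, 10% imputed).** p = 0.049 at base, 0.048 with 1.8 in both arms, 0.080 with 1.8 in the high arm only, and 0.078 under the both-arm worst case.

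**The case against.** The plan is not without a stress test. The worst case gives every missing high-trough subject the most extreme outcome, and at planning rates its 3-point loss exceeds the 1.7 points of the high-arm-only 80% run. In the borderline example it would also raise the alarm (p = 0.078). A reader might infer from the uniform inflation that nothing planned pulls the difference toward zero; the protocol's worst case shows that this is wrong. What stands is narrower. That run penalises the low arm as well, it sits at an extreme with no graded arm-specific steps before it, and the SAP does not define it.

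A reader might also infer that the uniform series is built to favour the high-trough arm. The documents do not support that. The direction depends on dropout by arm, on bleed rates and on between-subject spread, none of which they give for the imputed subjects. If dropout were heavier on the intensive regimen, the planned series would move against it.

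The sizes are also small. Only subjects who refuse to give bleed data are imputed, data obtained after leaving count as observed, only the missing part of the window is filled, and a subject who already bled in the window cannot change category. The plan further repeats the imputation without post-study data and analyses ABR in the per-protocol set. All of this limits the size of the point, but none of these runs applies an assumption that is worse for high-trough dropouts alone.

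**Conclusion.** The point holds in a limited form. The graded sensitivity series applies one factor to both arms. At 40% versus 70% with equal 10% dropout it is close to uninformative about the treatment difference: 30.0 to at most 30.3 points. No planned run tests high-trough dropouts doing worse than their own arm's model while low-trough dropouts do not.

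The likely effect on the conclusion is small: at most about 1.7 points for a high-arm-only 80% increase at planning rates with 10% fully imputed, p about 0.004. It could decide how robustness is described if the observed difference is near the significance boundary or if more subjects are imputed than planned. The missing worst-case rule is a separate small gap: read as all-missing-bleed it gives p = 0.0065, and read as the bound against the effect it gives p = 0.10, on the same data. This is an inexpensive improvement and not a flaw in the primary analysis.

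**What to change.** - Keep the planned both-arm runs.
- Add to SAP 5.5.1.2 a series with the Poisson parameter raised by 10, 20, 40 and 80% in the high-trough arm only and the low-trough arm at the base imputation. Continue it as a tipping-point analysis until all missing high-trough subjects have a bleed, and report where significance is lost, if it is.
- State the worst-case rule in SAP 5.5 in line with Protocol 14.4.1: every subject with missing data in the window, in either arm, counts as having a bleed. The version against the effect (missing high arm bleeds, missing low arm bleed-free) can be an optional extra bound. It need not replace the protocol's rule.
- Show the number imputed and the imputed time by arm beside these results, since both size and direction depend on them.

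The cost is some SAP wording, a few reruns of the same program and one more sensitivity table, which may look less favourable than the planned ones.
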